#### 8.3.2 Hy's Law Cases

It is important to identify possible cases of Drug-Induced Liver Injury (DILI) early. Total bilirubin, AST, and ALT should be regularly monitored for elevations indicative of liver damage. Subjects who experience a transaminase elevation above three times the ULN should be monitored frequently to determine if the elevation is transient. Transient elevations are an indication of adaption and these subjects may be identified as "adaptors." However, should a transaminase elevation be followed by total bilirubin (TBili) increase, a DILI could be occurring. Any laboratory abnormalities meeting the following criteria should be reported within 24 hours of awareness:

• AST or ALT elevation > 3 x ULN; and

- Total bilirubin > 2 x ULN; and
- Absence of cholestasis; and
- No alternative explanation for the elevations (e.g., impaired glucuronidation capacity caused by genetic [Gilbert syndrome]; viral hepatitis A, B, or C, preexisting or acute liver disease; or another drug capable of causing the observed injury).

Investigators should conduct reasonable investigations to rule out other possible etiologies. Investigators should take into consideration the subject's use of ethanol, acetaminophen, recreational drugs, herbal supplements, and medical history. A potential Hy's Law case will not be considered a confirmed case until all results and considerations have excluded alternative etiologies.

Possible cases of DILI will be promptly reported to the FDA and Repare Therapeutics prior to full work up to rule out other etiologies. Reporting should be completed on a MedWatch 3500A form and should include all available information, including the likelihood that the drug caused the event. Subjects should be closely followed until the resolution of the event.

Subjects who experience possible DILI should be managed per the Dose Modification Guidelines.

#### 8.4 Data Safety Monitoring Committee

A Data Safety Monitoring Committee (DSMC) at HCI is charged with ensuring the risk/benefit balance for subjects undergoing study therapy. The purpose of the DSMC is to ensure subject safety and make recommendations for study conduct to ensure subject safety and data integrity. The DSMC is chaired by a medical oncologist and may include, but is not limited to, representatives from medical oncology, oncological sciences, biostatistics, and pharmacy.

The roles and responsibilities of the DSMC are described in the NCI-approved Data and Safety Monitoring (DSM) plan. The activities of the committee include reviewing adverse events (including SAEs), deviations, important medical events, and approving cohort/dose escalations. Amendments that increase risk, increase treatment exposure, or impact study objectives will also be reviewed by the DSMC. If the DSMC and/or the PI have concerns about unexpected safety issues or AE trends, the study may be stopped and an unplanned safety data analysis may be conducted. Enrollment will not resume until the issues are resolved. The DSMC also reviews and approves audit reports generated by the Research Compliance Office.

All trials will be assigned and an oncologist member of the DSMC to serve as a medical monitor. In rare cases, an external medical monitor may be assigned. The Medical Monitor will be notified of all serious adverse events (SAEs). Specific notifications will also be issued when a dose-limiting toxicity is encountered and when the RP2D is defined. Approval from the Medical Monitor is required for all dose escalations. All serious adverse events (SAEs) occurring in subjects treated at HCI or its affiliates will also be reviewed by the full DSMC monthly.

Each trial is assigned a research compliance officer who will be responsible for monitoring the trial and reporting to the DSMC. The assessed risk level of the trial will determine the frequency with which monitoring occurs. The Research Compliance Officer monitor will review the study status and summarize enrollment, toxicities, SAEs, dose-escalation, statistical endpoints (e.g.,

stopping rules), deviations, and any other pertinent information for the full DSMC membership at the regularly scheduled meetings.

Audits will be conducted for all trials one year after enrollment begins and annually thereafter. Audits may be conducted more frequently as requested by the DSMC, Institutional Review Board (IRB), Protocol Review and Monitoring Committee (PRMC), Research Compliance Office management, or the Principal Investigator.

DSMC oversite will be tailored to the assessed risk level of the trial. Trials are categorized amongst three risk levels: high, moderate, and low.

This trial has been classified as high risk and therefore will be monitored by RCO and reviewed by DSMC after the first subject is enrolled and then quarterly thereafter.

# 9 STATISTICAL CONSIDERATIONS

9.1 Sample size determination

#### 9.1.1 Number of Patients Required for Dose Expansion

Prior to amendment v. 28AUG2023, five patients were treated at the previous DL1 (camonsertib 40mg daily and olaparib 100mg BID dosing 3 days per week). It was determined that this dosing strategy may not be appropriate for R/R CLL patients and reduced dosing may be necessary to increase safety of the combination therapy. These patients will be replaced and will not be included in the analysis.

The planned sample size for dose expansion is 24 evaluable patients with a primary endpoint of overall response rate (ORR). In a recent phase I/II study of pirtobrutinib enrolling a similar CLL patient population, the ORR of the drug was 63%. Therefore, the target ORR for the dose expansion portion of the trial will be 60%. ORR will be summarized by the observed proportion and an exact one-sided 95% confidence interval (Clopper-Pearson method). The estimated ORR and lower bounds of the confidence interval with 24 patients and ORR near 60% is presented in Table 19. With 24 evaluable patients, the lower bound of the confidence interval will be approximately 17-20% below the observed proportion for observed ORR near 60%, which is an acceptable level of precision in a dose expansion cohort.

Lower Bound of a One-sided 95% Confidence Interval for ORR with N = 24 Patients			
Number of Objective ResponsesObserved ORRLower Bound of one side 95% Confidence Interval			
10	42%	24%	
11	46%	28%	
12	50%	31%	

13	54%	35%
14	58%	39%
15	63%	43%
16	67%	47%
17	71%	52%
18	75%	56%

# 9.1.1.1 Enrichment of Dose Expansion with del(11q) and ATM Mutated Patients

An enrichment cohort of 8 patients with either del(11q) and/or ATM mutation will be included in the arm A dose expansion cohort. If 8/8 patients in the enrichment cohort are responders, the lower bound of the exact one-sided 95% confidence interval will be 68.7%. If 7/8 are responders, the lower bound is 52.9%.

#### 9.2 Populati on for Analyses

A modified intent-to-treat data set will be used for both safety and efficacy endpoint analysis. All subjects who havereceived one dose of study medication will be included in all efficacy and safety data sets. Subjects who fail to begin study therapy will be replaced.

# 9.2.1 DLT Evaluable Population

For dose-finding, subjects who receive at least one dose of any study drug during the DLT evaluation period will be considered evaluable for a DLT event. Only subjects who have experienced a DLT event or received 80% of the expected doses during the DLT period will be included when evaluating dose level changes.

#### 9.2.2 Population for Sensitivity Analyses

#### 9.2.2.1 Per Protocol Analysis

An additional analysis will be conducted including all subjects who have had an on treatment response assessment including imaging studies. All subjects without an on treatment response assessment will be excluded from this analysis.

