## 6.9.1 Criteria for the Discontinuation of Treatment

Subjects may withdraw from treatment or the study overall at any time at their request, or they may be withdrawn at the discretion of the Investigator or Sponsor for safety, behavioral reasons, or the inability of the subject to comply with the protocol-required schedule of study visits or procedures. In addition to the drug-specific discontinuation criteria listed in section 7, the following will result in treatment discontinuation:

• The subject requests to discontinue the study treatment and/or study procedures;

- Clinical deterioration that, in the opinion of the investigator, increases the risk to the subject;
- Confirmed disease progression based on iwCLL 2018 criteria (Section 7.5.3);
- Adverse events or intercurrent illness that in the opinion of the investigator warrants the subject's withdrawal from study treatment;
- Significant noncompliance with the protocol schedule or treatment administration in the opinion of the investigator;
- Pregnancy;

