# 7.4.2 Disease Assessment Algorithm

All patients should have a CT scan of the neck, chest, abdomen, and pelvis with IV contrast at the time of screening or up to 28 days prior to C1D1. CTs are required at C4D1 (± 7 days). Should this CT show that the patient has achieved an iwCLL 2018 defined complete remission (CR) and absolute lymphocyte count is <4000, then a bone marrow biopsy should be performed to confirm CR.

At any other study time point beyond C4D1 excluding end of treatment, the patient may have a disease assessment if the subject achieves hematologic recovery or the treating physician suspects the patient has achieved a CR as per the 2018 iwCLL criteria. At that time, a peripheral blood immunophenotype should be ordered. If the peripheral blood

immunophenotype shows no evidence of circulating CLL cells, then CTs of the neck, chest, abdomen, and pelvis should be performed. Should the CT also confirm CR, then a bone marrow biopsy should be performed to confirm CR. The study team has 28 days to complete all necessary testing required to confirm a CR from the time a CR is suspected by the treating physician. During this time, protocol treatment may continue as prescribed.

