# 7.5.3 Progressive Disease

Progressive disease during or after therapy is characterized by at least one of the following:

- Lymphadenopathy: Progression of lymphadenopathy as confirmed by physical examination. Disease progression occurs if one of the following events is observed:
  - Appearance of any new lesion, such as enlarged lymph nodes (≥ 1.5 cm), splenomegaly, hepatomegaly, or other organ infiltrates.
  - An increase by 50% or more in greatest determined diameter of any previous site.
- Splenomegaly: An increase in the spleen size by ≥ 50% of the extent of enlargement of the spleen below the costal margin or the de novo appearance of splenomegaly defined by palpation. If no prior splenomegaly was observed at baseline or if splenomegaly has resolved with treatment, the spleen must increase by at least 2 cm from baseline.
- An increase in the liver size of ≥ 50% of the extent enlargement of the liver below the costal margin defined by palpation, or the de novo appearance of hepatomegaly. Given the impact of numerous medical conditions, liver size by physical examination or by CT scan is not a reliable measure of hepatic involvement by CLL and should only be counted if hepatomegaly is clearly attributable to lymphoid involvement.
- An increase in the number of blood lymphocytes by 50% or more with at least 5 x 10^9/L B lymphocytes.
- Transformation to a more aggressive histology (e.g., Richter syndrome or Richter transformation). Whenever possible, this diagnosis should be established by lymph node biopsy.

- Occurrence of cytopenia (neutropenia, anemia, or thrombocytopenia) directly attributable to CLL and unrelated to autoimmune cytopenias.
  - During Therapy: Cytopenias may occur as a side effect of many therapies and should be assessed according to CTCAE criteria. During therapy, cytopenias cannot be used to define disease progression. Dose reductions for cytopenias are outlined in Section 6.
  - After Treatment: The progression of any cytopenia (unrelated to autoimmune cytopenia), as documented by a decrease of Hb levels by ≥ 20 g/L (2 g/dL) or < 100 g/L (10 g/dL), or by a decrease of platelet counts by ≥ 50% or to < 100 x 10^9/L, which occurs at least 3 months after treatment, defines disease progression, if the marrow biopsy demonstrates an infiltrate of clonal CLL cells and is not considered treatment-related toxicity.

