# 9.4.2 Overall Response Rate

Overall response rate (ORR) will be calculated as the sum of subjects achieving any complete response (including CR and CRi) or any partial response (including PR and nPR) divided by the total number of response evaluable subjects. Subjects without a baseline/screening tumor assessment or at least one on-treatment assessment will be considered non-responders. Each value will be reported along with a one-sided 95% exact binomial confidence interval. No hypothesis testing will be performed for ORR.

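### The per-protocol sensitivity set in 9.2.2.1 can drop treated patients who fail before their first CT, so its ORR is expected to run high; the primary ORR is not affected

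*Combined protocol and SAP*

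**What the plan says.** The main efficacy set (9.2) is modified intention-to-treat: "All subjects who havereceived one dose of study medication will be included in all efficacy and safety data sets". For the primary endpoint, 9.4.2 adds: "Subjects without a baseline/screening tumor assessment or at least one on-treatment assessment will be considered non-responders".

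Section 9.2.2.1 then sets up a per-protocol sensitivity population in two sentences. The first admits patients: "An additional analysis will be conducted including all subjects who have had an on treatment response assessment including imaging studies". The second removes the rest: "All subjects without an on treatment response assessment will be excluded from this analysis". The first sentence requires imaging and the second does not mention it. Neither defines on treatment, and neither makes an exception for progression, death or toxicity. The section does not name an endpoint; I read it as applying to ORR, since the set is defined by response assessment.

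On the timing of the first on-treatment CT, 7.4.2 says "CTs are required at C4D1 (± 7 days", while footnote 20 of the Schedule of Events places it at C5D1. These two places need to be reconciled.

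Progression does not need a scan. Section 7.5.3 begins "Progressive disease during or after therapy is characterized by at least one of the following" and lists, among others, nodes on examination, palpable spleen, lymphocyte count and transformation. Section 6.9.1 lists as a reason to stop treatment: "Confirmed disease progression based on iwCLL 2018 criteria (Section 7.5.3". It also allows withdrawal for adverse events or clinical deterioration.

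**The concern.** A patient who fails in the first 9 to 12 weeks is a known non-responder, yet may never have the on-treatment scan that admits a patient to this set. Membership then depends partly on the outcome being measured: patients who do well enough to reach the first CT are in, and some who fail before it are out. A sensitivity analysis built that way tends to move in one direction. It would place a more favourable figure beside the primary ORR, closer to or above the 60% target in 9.1.1. The set also says little about adherence to the protocol, despite its name.

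The neighbouring as-treated set (9.2.2.2) shows the contrast: there, doses missed to manage treatment-related toxicity do not cost a patient a place. Section 9.2.2.1 has no comparable protection.

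**Working it through.** **Inputs.** N = 24, target ORR 60%, exact one-sided 95% Clopper-Pearson bound (9.1.1); 21-day cycles (6.1); first CT at C4D1 (7.4.2) or C5D1 (Schedule of Events, footnote 20). The numbers of responders and of early failures are assumptions.

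**1. The plan's own bounds.** For x responders among n, the lower bound is the 5th percentile of Beta(x, n − x + 1). For n = 24 and x = 10 to 18 this gives 24.6, 28.2, 31.9, 35.8, 39.7, 43.7, 47.9, 52.1 and 56.5%. The table in 9.1.1 prints 24, 28, 31, 35, 39, 43, 47, 52 and 56%, the same values cut to whole percents. The plan's figures reproduce.

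**2. Time at risk before the first CT.** C4D1 is day 3 × 21 + 1 = 64; C5D1 is day 4 × 21 + 1 = 85. The gap is 63 to 84 days, or 9 to 12 weeks.

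**3. Effect of excluding k unscanned non-responders.** The primary ORR stays at x/24; the sensitivity ORR becomes x/(24 − k). With x = 14:

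| k excluded | ORR | Lower bound |
|---|---|---|
| 0 | 14/24 = 58.3% | 39.7% |
| 1 | 14/23 = 60.9% | 41.7% |
| 3 | 14/21 = 66.7% | 46.4% |
| 4 | 14/20 = 70.0% | 49.2% |

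With x = 12 (50.0%), k = 3 gives 12/21 = 57.1%, and k = 4 gives 12/20 = 60.0%, equal to the target.

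**4. Is k = 3 plausible?** Section 6.5 removes dose-escalation patients with a DLT from protocol, and the DLT window is cycle 1 (4.2.4), before any scheduled response CT. Up to 12 patients treated at the RP2D can carry over into phase II (4.3). In the decision table in 4.2.3, a stay decision at 12 patients corresponds to exactly 3 DLTs. Also, 4.4 expects 9 carried over; at the 30% target DLT rate that is 0.30 × 9 = 2.7. So k = 3 fits the plan's own figures, provided those patients are non-responders and their EOT CT does not count.

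**5. Direction.** Suppose m patients are excluded, a of them responders. The sensitivity ORR is (x − a)/(24 − m), which exceeds x/24 exactly when a/m < x/24. With x = 14, it rises if fewer than 58.3% of those excluded are responders. For m = 3, a = 1 gives 13/21 = 61.9% (higher), and a = 2 gives 12/21 = 57.1% (lower).

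**The case against.** The strongest reply is that nothing important rests on this set. A reader might infer that the trial's headline ORR is inflated; the documents do not support that. Section 9.2 includes every dosed subject, 9.4.2 plans no hypothesis test, and no go/no-go rule refers to 9.2.2.1. The denominator in 9.4.2 ("divided by the total number of response evaluable subjects") is undefined, but its rule for unassessed subjects would have no effect unless they were counted in it. This reply stands and limits the severity.

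A reader might also infer that every early progressor and toxicity withdrawal is certain to leave the set. That too goes beyond the text. Section 7.4.3 asks for an EOT assessment whatever the reason for coming off, and the Schedule of Events includes a CT there. The schedule lists EOT under the post-treatment period, but 4.5.1 has EOT assessments done in patients who continue treatment after cycle 18. If EOT CTs count, many of these patients stay in. The second sentence of 9.2.2.1, which omits imaging, could also be read as keeping a patient whose progression was documented by examination or blood counts. Only unscanned deaths leave on either reading of the EOT CT.

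Nor can it be said that the set can only raise the ORR. Section 7.5.2 allows elements of PR by palpation and blood counts, so a responder who was never scanned could leave too. Step 5 shows that responders would have to be most of those excluded to reverse the direction, which is unlikely.

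Larger effects can be computed: 6 exclusions give 14/18 = 77.8%. But that needs 6/24 = 25% of patients to fail unscanned, and 5.1.7 requires an expected survival of at least 12 months. The documents do not support it as an expectation.

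Finally, a response-assessed subset has some use beside the primary ORR, because it shows how much depends on counting unassessed patients as failures. That is fair, but such a set should be named for what it is and its exclusions explained.

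**Conclusion.** The concern holds for the sensitivity ORR only, and it is minor. As written, 9.2.2.1 lets known non-responders leave the denominator, so this ORR is expected to be biased upward. With 14 responders among 24, the rise is 2.5 percentage points for one exclusion, 8.3 for three and 11.7 for four. These sizes assume that all those excluded are non-responders. Beyond unscanned deaths, they also assume that EOT and unscheduled CTs, and assessments without imaging, do not admit a patient. The documents give no early-failure rate, so the size cannot be fixed; three is the case best tied to the plan's own design. The primary ORR is unchanged.

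**What to change.** Amend 9.2.2.1 as follows:

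- Keep in the set, as non-responders, all treated patients with progression by any 7.5.3 criterion, death, or discontinuation for toxicity or clinical deterioration before the first CT.
- Exclude only patients left unassessed for reasons unrelated to disease or study drug, such as consent withdrawn before the first assessment.
- State whether EOT and unscheduled CTs count as on treatment, and make the two sentences agree on whether imaging is required.
- Report the number excluded, with reasons, beside the primary ORR.

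It would help to define response evaluable in 9.4.2 at the same time and to reconcile the C4D1 and C5D1 CT timings.

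If three patients fail early for disease- or drug-related reasons, the amended set gives 14/24 = 58.3%. If one of the three was unassessed for an unrelated reason, it gives 14/23 = 60.9%.

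The cost is a wording change to protocol section 9, which needs IRB approval under 10.4, and a slightly less favourable sensitivity figure. Reasons for stopping study treatment should be in the study records, but the plan does not name a case report form field for them, so this should be confirmed.

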#### 9.2.2.2 As-treated Analysis

An as-treated analysis will be conducted including all subjects who have maintained at least 75% medication compliance. Subjects who have missed over 25% of the required doses during study therapy for any reason other than for the management of treatment-related toxicities will not be evaluable for this analysis.

# 9.3 Stopping Rules

The trial will be evaluated quarterly for excess toxicity. A rate of 20% grade 3 or higher non-hematological toxicity is acceptable, while a rate of 35% is unacceptable. Stopping boundaries were calculated using the R function "toxbdry" in the package "clinfun". The trial will be stopped if more than 2/4, 3/8, 4/12, 5/16, 6/20, 7/24, 8/28 or 9/34 patients experience grade 3 or higher non-hematologic adverse events attributed to study therapy during the 12 month evaluation period.

The operating characteristics of the stopping rule are difficult to determine precisely because up to 12 patients from the phase Ib portion will contribute to the phase II. We evaluated the operating characteristics in two ways. First, we present operating characteristics of the stopping rule calculated by toxbdry(0.16, 0.4, c(4,8,12,16,20,24,28,34),cP0=0.1, cP1=0.9, ngrid=7) in Table 20. This table assumes the operating characteristics are unaffected by the patients carried over from phase Ib to phase II. Second, we explore the effect of the rollover from phase Ib to phase II. Second, we explore the effect of the rollover from phase Ib to phase II with a scenario in which the dose selection has a relatively large effect (Table 21). There are 3 assumptions: 1) 12 patients from the phase Ib portion contribute to phase II, 2) all of the grade 3 or higher non-hematologic toxicity occurred in the 28 day DLT period of phase Ib, and 3) the observed toxicity in the 12 rollover patients is in the target range of 25-35%. It is noted that the stopping probability in Table 21 is higher than the corresponding stopping probability in Table 20 when the true toxicity is lower than the target, and lower when the true toxicity is higher than the target.

Operating Characteristics of Stopping Rule Calculated by toxbdry			
Probability of DLT	Probability of Crossing Boundary	Probability of Stopping Before Last Patient	Expected Sample Size
0.16	8.9%	7.9%	32.3
0.20	21.1%	18.0%	30.4
0.24	38.9%	32.8%	27.6
0.28	58.4%	50.1%	24.1
0.32	75.5%	66.7%	20.5
0.36	87.6%	80.2%	17.2
0.40	94.6%	89.6%	14.3

Table 20: Operating C haracteristics of Stopping Rule from toxbdry (N = 34)

Table 21: Operating Characteristics of Stopping Rule Under Scenario (N = 34)

Operating Characteristics of Stopping Rule under the Scenario Described Above

Probability of DLT	Probability of Crossing Boundary	Probability of Stopping Before Last Patient
0.16	13.7%	11.3%
0.20	26.3%	20.7%
0.24	41.9%	32.9%
0.28	58.9%	47.3%
0.32	73.3%	60.6%
0.36	84.4%	72.8%
0.40	91.4%	82.3%

Should a treatment-related death occur on study, the trial will be stopped until all investigators and the DSMC can meet and determine appropriate actions. The event will be reported to the FDA.

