### 4.3 Phase II Dose Expansion

After completion of the phase Ib portion and assignment of the RP2D, continuous enrollment of patients may commence into the phase II dose expansion portion. All patients enrolled at the RP2D during the phase Ib dose-escalation portion of the trial can be carried over into the phase II analysis. The maximum number of patients that can be carried over from the dose escalation to the dose-expansion portion is 12.

The phase II dose expansion will consist of two separate cohorts of subjects: an enrichment cohort and a cohort for all other eligible subjects. All subjects enrolled into the enrichment cohort must have a del(11q) and/or ATM mutation. Eight subjects will be enrolled into the enrichment cohort and 16 will be enrolled into the second cohort for a total phase II cohort of 24 patients.

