### 4.4 Study Duration and Sample Size

With cohorts of 3 patients and possible early completion of the dose-escalation due to a DL accruing 12 patients, then the minimum time to accrue 4 cohorts is 4 months. Due to potential delays in patient enrollment and variability in dose escalation cohort size, the maximum enrollment time frame for the dose escalation portion is anticipated to be 24 months. Expansion at the RP2D is anticipated to be between 6-12 months as a portion of the dose escalation cohort treated at the RP2D will be rolled into the expansion cohort. Therefore, the total study duration is between 12-36 months, which is inclusive of the phase Ib and phase II durations.

On average, we expect 33 patients to be enrolled, assuming that 9 patients in the phase Ib portion will be treated at the MTD and rolled into the dose expansion phase. If the dose escalation portion enrolls patients only at the RP2D and all of these patients are rolled into the dose-expansion cohort, then the minimum number of patients required would be 24 for the entire trial. The maximum number of patients required would be 39 assuming that only 3 patients roll over from the dose escalation to the dose expansion.

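### The toxicity stopping rule is described as 20% acceptable and 35% unacceptable but was built for 16% and 40%, and Table 21 runs it to 34 patients when phase II ends at 24

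*Combined protocol and SAP*

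**What the plan says.** Section 9.3 sets a trial-level rule for grade 3 or higher non-hematologic events attributed to study therapy, evaluated quarterly. It states: "A rate of 20% grade 3 or higher non-hematological toxicity is acceptable, while a rate of 35% is unacceptable". The trial stops if the count exceeds 2, 3, 4, 5, 6, 7, 8 or 9 at 4, 8, 12, 16, 20, 24, 28 or 34 patients. The call that gave the operating characteristics is printed as "toxbdry(0.16, 0.4, c(4,8,12,16,20,24,28,34),cP0=0.1, cP1=0.9, ngrid=7".

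Table 20 gives the operating characteristics to 34 patients and ignores the rollover. Table 21, also to 34, gives them for a scenario in which "12 patients from the phase Ib portion contribute to phase II" and 25-35% of those 12 have already had an event.

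The sizes are given elsewhere:

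- Section 4.3 plans 8 plus 16 patients "for a total phase II cohort of 24 patients". It also says: "The maximum number of patients that can be carried over from the dose escalation to the dose-expansion portion is 12".
- Section 4.4 says "On average, we expect 33 patients to be enrolled", and "The maximum number of patients required would be 39 assuming that only 3 patients roll over from the dose escalation to the dose expansion".
- Section 9.1.1 says of the five patients treated on the earlier schedule: "These patients will be replaced and will not be included in the analysis".

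**The concern.** There are two separate problems.

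**Rates.** The text names one pair of rates and the boundary was computed from another. A reader who takes 20% and 35% as the design rates would expect the 10% and 90% crossing targets to apply there. The result at 20% is printed in Table 20. The result at the plan's own unacceptable rate appears in neither table.

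**Size.** Section 9.3 does not say which patients are counted. The last look, at 34, equals none of the totals the plan names (24, 33, 39). Table 21 combines 12 rollovers with 34 patients, which Section 4.3 does not allow.

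The trial is classed as high risk, and stopping rules are among the items summarized for the DSMC. If monitoring in fact ends earlier than 34, the rule protects less than the tables show. If it covers every patient and the trial grows past 34, the last patients have no boundary.

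**Working it through.** **Inputs.** From Section 9.3: looks at n = 4, 8, 12, 16, 20, 24, 28, 34, with a stop when the count reaches 3, 4, 5, 6, 7, 8, 9, 10. From Section 4.2: phase Ib of 18. From Section 4.3: phase II of 24 including at most 12 rollovers. From Section 4.2.5.3: an optional extension of phase Ib to 24.

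**Method.** Exact binomial recursion. With f(k) the probability of having continued with k events, and m new patients before the next look,

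f_next(k) = Σ_j f(k−j) · C(m,j) p^j (1−p)^(m−j).

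At each look the mass at or above the limit is added to the crossing probability and removed.

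**Step 1: reproduce Table 20.** The recursion gives 8.9, 21.1, 38.9, 58.4, 75.5, 87.6 and 94.6% at 16, 20, 24, 28, 32, 36 and 40%. All seven match the printed crossing column. At 35%, which has no row, it gives 85.0%, so 100 − 85.0 = 15.0% of trials at that rate run to the end unstopped.

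**Step 2: reproduce Table 21.** Start at 12 patients with 3 or 4 events (3/12 = 25%, 4/12 = 33.3%), weighted by their binomial probabilities, then look at 16, 20, 24, 28 and 34.

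| True rate | Printed | Recomputed to 34 |
|---|---|---|
| 16% | 13.7% | 13.4% |
| 20% | 26.3% | 26.3% |
| 24% | 41.9% | 42.4% |
| 28% | 58.9% | 58.9% |
| 32% | 73.3% | 73.3% |
| 36% | 84.4% | 84.3% |
| 40% | 91.4% | 91.7% |

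Agreement is within 0.5 point. The table therefore describes 12 rollovers plus 34 − 12 = 22 further patients.

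**Step 3: which sizes are possible?** In phase II, 12 rollovers leave 24 − 12 = 12 new patients. Over the whole trial, with r rollovers, the total is 18 + 24 − r:

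- r = 3 gives 39
- r = 8 gives 34
- r = 9 gives 33
- r = 12 gives 30

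The five earlier patients are excluded. With 12 rollovers, 34 is reached only under the optional extension: 24 + 24 − 12 = 36.

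**Step 4: rerun at those sizes.**

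| Start and last look | 20% | 35% | 40% |
|---|---|---|---|
| Table 20 start, to 34 | 21.1% | 85.0% | 94.6% |
| Table 20 start, to 28 | 18.0% | 77.2% | 89.6% |
| Table 20 start, to 24 | 16.6% | 72.2% | 85.7% |
| Table 21 start, to 34 | 26.3% | 81.9% | 91.7% |
| Table 21 start, to 28 | 20.8% | 69.8% | 82.2% |
| Table 21 start, to 24 | 17.8% | 61.1% | 74.0% |

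At the expected total of 33, the last scheduled look reached is 28, which gives 77.2% at 35%. Applying the limit of more than 9 events at patient 33 raises this to 83.1%.

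**Step 5: could 10% and 90% be met at 20% and 35%?** A single look at 34, stopping at 11 or more, gives 6.2% and 68.7%. The smallest single-look size that meets both targets is 61 (stop at 17 or more: 8.8% and 90.5%).

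**The case against.** The strongest reply is that nothing is miscalculated. Both tables reproduce, and Section 9.3 never claims 10% and 90% at 20% and 35%. Those targets appear only inside the call that also shows 16% and 40%. The one-in-five stop at 20% is printed, and the rows at 32% and 36% (75.5% and 87.6%) bracket the missing 35% result. All of this stands. It makes the first part an unreconciled description, not a wrong boundary.

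On size, Section 9.3 speaks of stopping the trial and schedules looks at 28 and 34, neither of which can occur in a set of 24. Section 9.2 puts every treated patient in the safety data set. A trial-wide reading is therefore available. On that reading a total of 34 is ordinary, and the gap after 34 arises only with seven or fewer rollovers. At 33 patients, 83.1% is a fair figure, because more than 9 events by then already guarantees a crossing at 34. These points stand too, so the 24-patient figures are conditional. But the section's own language about rollovers contributing to phase II points the other way, and the section does not settle it.

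Table 21 is presented as one scenario with a relatively large effect, and the keyboard rule, the halt after a treatment-related death and DSMC review give further protection. That limits the harm, but it does not make 12 rollovers and 34 patients compatible with the main plan. Table 21's column for stopping before the last patient (82.3% at 40%) does match a last look at 28, but it is not labelled as the result for a 30-patient trial.

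**Conclusion.** Both parts hold. The printed boundary is a 16%/40% rule. At the rates in the text it stops 21.1% of trials when toxicity is acceptable and 85.0% when it is unacceptable, if all 34 patients are monitored.

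Table 21's composition is impossible without the optional extension of phase Ib. Cut to the 24 patients of phase II, its stopping probability at 40% falls from the printed 91.4% to 74.0%, about 17 points, and it is 61.1% at 35%. On the trial-wide reading with 12 rollovers (30 patients, last look 28), the figures are 82.2% and 69.8%. Without the rollover start, ending at 24 gives 72.2% at 35%, so about 28% of such trials would not be stopped.

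These results assume independent patients with a common event rate and looks exactly at the listed counts. The 24- and 30-patient figures also depend on which patients are counted, which the plan must say. The fault lies in the description and in one table's scenario, and it should be fixed because the DSMC relies on this rule.

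**What to change.** - **Rates.** Either state 16% and 40% as the rates used to build the boundary and say how they relate to 20% and 35%, or keep the text and report the actual stopping probabilities there (21.1% and 85.0% at 34). In either case add a 35% row to Tables 20 and 21. Rebuilding for 10% and 90% at 20% and 35% is not feasible at the planned size, so restating is the cheap route.
- **Population.** Say whether the rule counts phase II including rollovers, or all patients on the current dose levels.
- **Looks.** End them at that population's planned size (24 for phase II, up to 39 for all patients), and recompute both tables with a rollover scenario that fits.
- **Text.** Reconcile the 25-35% target range in Section 9.3 with 25-33% in Section 4.2, and the 28-day DLT period in Section 9.3 with the Day 1 to Day 21 window in Section 4.2.4. Correct the column heading that refers to DLT, since the rule counts grade 3 or higher non-hematologic events.

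The cost is one rerun, two revised tables and some wording. No patients are added. The reported stopping probabilities at the unacceptable rate will look less favourable.
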